1.3 Clinical Data to Date

The 2011 Wall et al. open-label trial (conducted under IDE number G060269) that treated a total of 7 antidepressant-resistant adolescents demonstrated a robust response rate noted by 5 of 7 subjects achieving remission of depression as rated by the Childhood Depression Rating Scale - Revised (CDRS-R). Furthermore, CDRS-R mean depression severity responses were noted to be significant by treatment #20 with correlated improvement as demonstrated with the self-report Quick Inventory of Depressive Symptoms – Adolescent Version (QIDS-A17-SR) (Figure 1). Placebo response rates in open-label trials of adolescents are a well-known phenomenon. However, the adolescents treated in our initial protocol demonstrated enduring mood improvement 6 months following their final treatment session. Furthermore, 7 of 8 subjects completed the entire treatment course – with 1 dropping out after a total of 5 minutes of treatment due to scalp discomfort and a perceived “lack of improvement”.

Figure 1 – CDRS-R and QIDS-A17-SR Response in Depressed Adolescents in an Open-label rTMS Trial (Wall, et al. J Clin Psychiatry, 2011. 72(9): p. 1263-1269

Evidence from the currently proposed study would extend these initial findings and begin to answer questions relating to the neurobiological basis of those who show response or remission of depression with rTMS treatment and those who do not respond.

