4.4.2 Data Collection and Follow-up for Withdrawn Subjects

To enhance the validity of study data, as well as to provide subjects with ongoing monitoring and safety assessments by a qualified professional, subjects who choose to withdraw from the interventional portion of the study will be offered the opportunity to complete mood, cognitive, safety, and imaging assessments as per the study protocol.

5 Study Device

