7.1 Sample Size Determination

Preliminary data from the 2011 Wall et al. pilot study[1] was used to estimate the sample size needed per treatment group to achieve at least 80% power for detecting a difference between the active and sham treatments using 2 versions of the CDRS-R depression inventory measured at baseline and completion of 30 sessions including: 1) the rate of those responding to treatment based on a CDRS-R and CGI-I finite cutoff score (binary), and 2) the raw change in CDRS-R score from baseline (continuous).

For the binary response we observed a success rate of 71% in our preliminary study. For sample-size purposes we hypothesize a success rate of 65% for rTMS. We further hypothesize a success rate of 25% for the Sham group. Based on these assumptions, we have determined that a total sample-size of N=70 (35 per group) will provide statistical power (two-tailed, alpha=0.05) of 94% to detect a difference between groups.

When the change in CDRS-R was quantified using a continuous variable we observed a mean delta of 33.3 with corresponding standard deviation of 7.3. Under the conservative assumption that the “true” standard deviation of this response is 10.0, we have determined that a total sample-size of N=70 (35 per group) will provide statistical power (two-tailed, alpha=0.05) of 91% to detect a difference between groups of 8.0 units.

Thus a total sample-size of N=35 per group will provide adequate statistical power. Since the primary analysis will be performed using the approach of LOCF, we will not adjust the sample-size to account for attrition. We will however, perform supplementary analyses which are restricted to subjects who complete the study. Under the assumption that the attrition rate is approximately 30% we repeated the power analyses described above using an effective sample-size of N=50 (25 per group). Using these effective sample-sizes, the supplemental

analysis restricted to study completers will have statistical power of 83% to detect the hypothesized difference when change in CDRS-R is quantified as a binary response and statistical power of 80% to detect a difference between groups of 8.0 units when the change in CDRS-R is quantified as a continuous variable.

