7.3 Subject Population(s) for Analysis

The primary analysis will use the intention-to-treat (ITT) population, defined as all patients who started at least one treatment session. Secondary analyses of the primary outcome will examine “completer” and “partially adherent” cohorts. The Completer Cohort will be defined as subjects treated according to the protocol with fewer than 10 rescheduled, missed, or partially completed rTMS sessions ultimately taking part in 30 treatment sessions. The Partially Adherent Cohort will have at least 20 completed or partially completed sessions without reaching the full 30-treatment threshold. Those with less than 20 completed or partially completed rTMS sessions will be analyzed within the intention-to-treat population.

8 Safety and Adverse Events

All Unanticipated Adverse Device Effects (UADEs) and severe, expected adverse events (AEs) at least probably related to the study treatment not meeting the criteria of UADE, including mania, exacerbation of depression, and suicidality will be recorded on the Adverse Event CRF and reported according to severity and the relationship of the AE to rTMS. Records of these events will be maintained and reports submitted to the FDA, regulatory sponsor, and reviewing IRBs according to local IRB policy and regulatory requirements. All other expected clinical adverse events and nonsignificant (not serious) clinical adverse events will be reported to all Principal Investigators on a periodic basis and reported to the appropriate IRB at the time of continuing review and to the FDA at the time of the Annual Report. Expected clinical adverse events and anticipated adverse device effects are those listed in Section 1.5.2.

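### Carrying the last rating forward as the primary missing-data method shrinks the active-sham difference at treatment 30 and shifts it whenever dropout differs between arms, and no planned analysis tests this

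*Combined protocol and SAP*

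**What the plan says.** Section 7.1 states that "the primary analysis will be performed using the approach of LOCF" and gives this as the reason for not adjusting the sample size for attrition. The same section puts attrition at about 30%, without a split by arm, and adds "supplementary analyses which are restricted to subjects who complete the study", for which power is given at 25 per group.

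Section 7.3 sets the primary population as intention-to-treat, "defined as all patients who started at least one treatment session", so very early dropouts are included. Completer and partially adherent cohorts are secondary. LOCF is not mentioned in 7.2 or 7.3, and no analysis varies the missing-data assumption.

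Section 7.2 describes a logistic regression of response on treatment number (10, 20, 30) and gender. It names no arm term, no within-subject correlation and no missing-data method.

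CDRS-R and CGI-I are scheduled after treatments 10, 20 and 30 (3.2.1, Table 4) and also at early withdrawal (Table 4 footnote g, 6.2.8). Under 4.4.2, subjects who stop treatment "will be offered the opportunity to complete mood, cognitive, safety, and imaging assessments as per the study protocol".

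**The concern.** LOCF treats the last available score as if it were the treatment-30 score. That is harmless only if scores have stopped moving. Here they are expected to move a great deal: 7.1 cites a pilot mean change of 33.3 units. Each dropout therefore enters the primary comparison with only part of the expected improvement. Two things follow. Equal dropout scales down a true difference. Unequal dropout creates or distorts a difference, because one arm contains more truncated courses than the other.

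Unequal dropout is plausible in either direction. Section 1.3 reports that 7 of 8 pilot subjects completed, "with 1 dropping out after a total of 5 minutes of treatment due to scalp discomfort" and a perceived lack of improvement. Discomfort could raise dropout on active stimulation, since the sham sensation is described as painless (3.1). Lack of improvement could raise it on sham. At stake are the size of the primary estimate, its power and its type I error.

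**Working it through.** **The plan's own figures.** Continuous endpoint, 35 per group, difference 8.0, SD 10: standard error = 10 × √(2/35) = 2.390; 8.0/2.390 − 1.96 = 1.387, giving 91.7% (t-test 91.0%; plan 91%). Binary endpoint, 65% vs 25%, pooled variance: 93.7% (plan 94%). At 25 per group: 83.2% and 80.7% (plan 83% and 80%). The arithmetic in 7.1 is sound. The question is whether LOCF preserves the 8.0 and the SD of 10 that it uses.

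**Expected LOCF mean in an arm.** Let F be the full change at treatment 30, d the dropout proportion, and c the average fraction of F present in a dropout's carried score. Then

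E = F × [1 − d × (1 − c)].

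Assumptions not in the documents: 40%, 75% and 100% of the change is reached by treatments 10, 20 and 30; of the dropouts, 40%, 35% and 25% leave before treatments 10, 20 and 30; dropout is unrelated to outcome within arm; F = 25 active and 17 sham (the 8.0 difference comes from 7.1).

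- Case A, no withdrawal rating obtained: c = 0.40×0 + 0.35×0.40 + 0.25×0.75 = 0.3275, so 1 − c = 0.6725.
- Case B, every dropout rated at withdrawal, taken as midway through the interval: c = 0.40×0.20 + 0.35×0.575 + 0.25×0.875 = 0.50, so 1 − c = 0.50.

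True difference 8.0:

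| Dropout active/sham | Case A | Case B |
|---|---|---|
| 30/30% | 8.0 × 0.798 = 6.4 | 8.0 × 0.85 = 6.8 |
| 40/20% | 25×0.731 − 17×0.8655 = 3.6 | 25×0.80 − 17×0.90 = 4.7 |
| 20/40% | 25×0.8655 − 17×0.731 = 9.2 | 25×0.90 − 17×0.80 = 8.9 |

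No true difference, shift = F × dropout gap × (1 − c):

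| Gap | F | Case A | Case B |
|---|---|---|---|
| 20 points | 17 | 2.3 | 1.7 |
| 20 points | 25 | 3.4 | 2.5 |
| 10 points | 17 | 1.1 | 0.85 |
| 10 points | 25 | 1.7 | 1.25 |

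**Power and rejection by simulation** (35 per arm, SD 10, within-subject correlation 0.7). With 30% dropout in both arms, power is about 59 to 60% in case A and 68% in case B. With no true difference, a 20-point gap (40/20%) gives 14 to 20% rejection in case A and 10 to 14% in case B. A 10-point gap (35/25%) gives 7 to 8% and 6 to 7%. Power falls by more than the shrinkage alone implies: 6.8 with SD 10 would still give 6.8/2.390 − 1.96 = 0.885, about 81%. The rest is extra spread, because carried scores mix subjects stopped at different points.

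**A different trajectory.** Take linear improvement to 33.3 active and 25.3 sham, correlation 0.6, and dropouts split equally between a last rating at treatment 10 and at 20. LOCF then gives 6.8 (30/30%), 33.3×0.80 − 25.3×0.90 = 3.9 (40/20%) and 33.3×0.90 − 25.3×0.80 = 9.7 (20/40%). Simulated power at 30/30% is about 61%, and null rejection at a 20-point gap is about 15%.

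**The alternative under the same linear trajectory.** A likelihood repeated-measures model returns 8.0 in every split, and 0.0 under the null, when dropout is random or depends on observed ratings; power is about 84 to 85%. When dropout depends on the unseen next rating, the model gives 7.1 (nominal 20/40%) and 8.9 (40/20%), with about ±1.0 under the null. LOCF in those settings gives 9.1 and 4.7, with about ±1.7.

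**Binary response.** Counting missing as nonresponse has the same weakness. With true response 45% in both arms and 40/20% dropout, 0.45×0.60 = 27% is compared with 0.45×0.80 = 36%. That is a spurious 9 points, rejected about 13% of the time.

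**The case against.** The best defence is that the schedule already softens the problem. Table 4 footnote g and 6.2.8 call for CDRS-R and CGI-I at withdrawal, so the carried score need not be a stale one. This stands, and it is why case B is shown: the shift is smaller but does not vanish, because a withdrawal score still reflects an unfinished course. Section 6.2 also lets subjects decline assessments, so case B is the favourable end.

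Second, a 20-point gap is a stress case. The documents give no split by arm, the pilot evidence is a single dropout among eight, and intensity reduction (1.4.2) and the open-label Phase II offer may limit dropout. This also stands: at a 10-point gap rejection is only 6 to 8%. It does not answer the loss at equal dropout, which needs no gap at all.

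Three stronger readings are tempting, and the documents do not support them.

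- A reader might infer that LOCF is undefined for CGI-I before treatment 10, since Table 4 has no pre-treatment CGI-I. The withdrawal assessment includes CGI-I, so the gap arises only when that visit is not done.
- A reader might infer that LOCF cannot use the later ratings offered under 4.4.2. Nothing in 4.4.2, 7.1 or 7.3 excludes them; the plan is silent on how they enter.
- A reader might infer that LOCF favours rTMS. With higher active dropout, the excess rejections mostly favour sham.

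**Conclusion.** The point holds. LOCF as the primary method is a poor match for an outcome expected to improve throughout treatment with about 30% attrition, and the plan contains nothing that would reveal the effect. The completer and partially adherent analyses change the population; they do not test the missing-data assumption.

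The attenuation and the direction of the shifts follow from continuing improvement. Their size rests on the assumed trajectory, dropout timing and arm split, none of which the documents give. The estimates above should be read as ranges, with the milder end requiring a withdrawal rating on every dropout. A repeated-measures model reduces the shift; it removes it only if dropout depends on observed ratings.

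**What to change.** In 7.1 and 7.2, make the primary CDRS-R analysis a repeated-measures model on change at treatments 10, 20 and 30, with arm, visit, arm-by-visit and baseline CDRS-R, allowing for within-subject correlation. The arm contrast at treatment 30 is the result. Enter withdrawal and post-withdrawal ratings at the matching time. Reconcile this with the logistic model in 7.2, so that one primary analysis is named and it contains an arm term.

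For binary response, use multiple imputation or a mixed logistic model with an arm term. Show missing-as-nonresponse only as a sensitivity analysis.

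Add a delta-adjusted or reference-based sensitivity analysis for dropout that depends on unseen ratings, and keep LOCF as a further sensitivity analysis. Reword the sentence in 7.1 that uses LOCF as the reason for not adjusting N.

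The cost is SAP wording and a little more analysis, settled before unblinding, with no new data. The price is reliance on a missing-at-random assumption in the primary result, which is why the sensitivity analyses belong beside it.

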7.2 Statistical Methods

Descriptive Statistics

Univariate descriptive statistics and frequency distributions will be calculated as appropriate for all variables. Baseline values for demographic, clinical, and outcome variables (primary and secondary) will be tabulated for the treatment groups. These analyses will help identify potential confounding variables to be used as covariates in sensitivity analyses. Distributions across subgroups used in randomization will be compared to assess whether the randomization was successful in equalizing distributions of these prognostic variables across treatment groups.

Statistically significant differences on overall comparisons will be explored using multiple pairwise comparisons of each of the (treatment) groups using Bonferroni correction for multiple comparisons. Mean scores and standard deviation for each group will be calculated.

Subsequent multiple comparisons via Tukey's procedure will be set at 0.01 to control Type I error rate.

Primary Hypotheses:

- 1) Adolescents in Phase I treated with active rTMS at the left dorsolateral prefrontal cortex (L-DLPFC) will have significant mood improvement when compared to sham treatment.
- 2) Adolescents in Phase II treated with maintenance rTMS at the L-DLPFC will achieve sustained response of the depressive symptoms.

Phase II represents a proof of concept/preliminary study of long-term maintenance for treatment responders (either active or sham in Phase I) and an opportunity for open-active treatment in nonresponders. The inclusion of phase II is ethically necessary to ensure that all pediatric participants are offered an opportunity to receive active treatment if unresponsive in phase I. The analysis of data collected as part of phase II is exploratory and will include primarily descriptive statistics.

Treatment outcomes for both phases will be defined as response (CDRS-R raw score <28 & CGI-I ≤2 & CGI-S ≤2), or nonresponse (CDRS-R raw score ≥28 and CGI-I ≥3) assessed using a logistic regression model with independent variables of treatment number (i.e. #10 vs. #20 vs. #30) and gender (male vs. female) will be analyzed. Assessing potential gender effects will be a secondary analysis. The primary analysis will not adjust for gender. Although we anticipate that more females than males will participate in the study, we assume that the distribution of gender will be similar between treatment arms and have no a priori reason to suspect that the efficacy of treatment will be gender specific.

Serious adverse events will be reported as noted within the application. All adverse events will be summarized according to treatment groups. Given the sample size for the current study, the statistical power for detecting differences between groups is limited. However, we will compare between groups using an exact test.

All statistical tests will be performed at the 0.05 significance level.

Secondary Hypotheses (for MCR site only):

Baseline glutamate, reported as a CSF-corrected absolute concentration and as an overlapping resonance with glutamine, will be significantly higher in both AC and L-DLPFC in depressed adolescents as measured by ^1H -MRS at 3T when compared to data derived from previously scanned healthy controls.

In comparison to non-remission subjects, depressed adolescents treated with rTMS who achieve remission (defined as a CDRS-R raw score <28 and CGI-I ≤ 2 and CGI-S ≤ 2 at treatment completion) will exhibit a greater decrease in glutamine, reported as a CSF-corrected absolute concentration percent change (baseline to endpoint) in AC and L-DLPFC as measured by ^1H -MRS at 3T.

The hypotheses will be tested using t-tests. Additionally, analyses of covariance will be performed to control for potentially important covariates or confounders, such as age or gender. Non-parametric distribution will be analyzed by non-ANOVA statistics.

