----------------------	---

Reference Therapy	Subjects in Phase I who are randomized to sham treatments will have schedules, systematic assessments, and treatment approaches that are identical to subjects randomized to active treatments. Subjects, treaters, and clinical raters will not know whether the treatment is active or sham in nature (double-blinded). The sham coil is identical in its appearance to the active coil. Furthermore, Neuronetics, Inc. has created an acoustic matching profile that renders the sensory experience of the treatments virtually indistinguishable to subjects or researchers. The acoustic signal creates a painless percussive sensation that will be felt by the subject and will assist in simulating the active condition.
Concomitant Therapy	
Permitted: Subjects are expected to be on stable dose pharmacotherapy with one of the antidepressants listed in protocol Section 4.1 (Inclusion Criteria). Any other medication change including initiation, discontinuation, or dose adjustment of medication, needs to be discussed with the site PI and approved before implementation.
 
Prohibited: Initiation of medication listed in protocol Section 4.2 (Exclusion Criteria) is not permitted during either phase of the study. Dose adjustment or initiation of permitted medications (Section 4.1 Inclusion Criteria) after enrollment must be approved by the site PI prior to implementation.

Statistical Methodology	
Statistical analysis plan for objectives 1, 2a, 2b : Treatment outcomes defined as remission, response, or nonresponse will be assessed using a logistic regression model with independent variables of treatment number (i.e. #10 vs. #20 vs. #30) and gender (male vs. female) will be analyzed at the 0.05 significance level. The primary outcome measures will include the CDRS-R and CGI-I.
 
Statistical analysis plan for objective 3 (data from MCR site only): The hypotheses will be tested using t-tests. Additionally, analyses of covariance will be performed to control for potentially important covariates or confounders, such as age or gender. Non-parametric distribution will be analyzed by non-ANOVA statistics.

1 Introduction

This document is a protocol for a human research study. This study will be carried out in accordance with the procedures described in this protocol, applicable United States government regulations, Mayo Clinic of Rochester (MCR), and the Medical University of South Carolina (MUSC) policies and procedures.

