Participants who do not meet criteria for response (CGI-I rating of 3 or greater and/or a CDRS-R score of 28 or greater) following Phase I treatment will be offered the opportunity for 30 treatments using the known-active coil. The treatment parameters and methods of assessment will be identical to those in Phase I. The only difference will be that the coil used for Phase II will be active and known to the subject, family, and investigators. See Table 5 for schedule of assessments.

Arm 2: Maintenance Treatment (Responder Cohort)

Subjects who, at the completion of Phase I, meet clinical criteria for treatment response (CGI-I rating of ≤ 2 and CDRS-R score of < 28) will be offered the opportunity for 52 weeks of maintenance rTMS treatment. The treatment parameters will be identical to those in Phase I treatment except for the frequency of visits (biweekly) instead of daily. Clinical assessments will be offered monthly throughout the duration of the maintenance phase. One final follow-up assessment will be scheduled for six months post final treatment. See Table 6 for schedule of assessments.

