6.3 Phase II – Non-Randomized, Open-Active

Study Overview

Subjects from Phase I will be offered the opportunity to continue with rTMS treatments in Phase II and assigned to treatment arms according to their clinical outcomes at the completion of Phase I. Adolescents from both the active and sham cohorts who do not meet clinical criteria for response (CDRS-R score ≥ 28 and/or CGI-I score ≥ 3) will be given active treatment (protocol Section 6.3.1). Subjects from both the active and sham cohorts who do meet response criteria (CDRS-R score of < 28 and CGI-I score of 1 or 2) will be given maintenance treatment (protocol Section 6.3.2).

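### The nonresponse rule in 7.2 is not the complement of its response rule: 5 of 8 score patterns get no code in the binary outcome, and CGI-S appears in that response rule but not in 7.1 or the Phase II rule

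*Combined protocol and SAP*

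**What the plan says.** In section 7.2 the favourable outcome, in both phases, is "defined as response (CDRS-R raw score <28 & CGI-I ≤2 & CGI-S ≤2". That rule has three conditions, all of which must be met. The unfavourable outcome has its own rule: "or nonresponse (CDRS-R raw score ≥28 and CGI-I ≥3) assessed using a logistic regression model". That one has two conditions, joined by *and*, and does not mention CGI-S.

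Other places give different rules:

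- **7.1**, the binary endpoint used for power: "the rate of those responding to treatment based on a CDRS-R and CGI-I finite cutoff score (binary". No cutoffs are given and CGI-S is not named.
- **3.1**, Phase II Arm 1: "Participants who do not meet criteria for response (CGI-I rating of 3 or greater and/or a CDRS-R score of 28 or greater". Here the conditions are joined by *and/or*, and 6.3 does the same.
- **6.3**, entry to Maintenance: subjects "who do meet response criteria (CDRS-R score of < 28 and CGI-I score of 1 or 2". There is no CGI-S term.
- **7.2**, secondary hypotheses: subjects "who achieve remission (defined as a CDRS-R raw score <28 and CGI-I" at most 2, with CGI-S also at most 2. These are the same three cutoffs as for response, yet the Study Summary lists three levels: "Treatment outcomes defined as remission, response, or nonresponse".
- **7.3**, the analysis population: "The primary analysis will use the intention-to-treat (ITT) population, defined as all patients who started at least one treatment session".

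The Summary names CDRS-R and CGI-I as primary outcome measures. Section 3.2.1 includes CGI-S among the Phase I measures.

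**The concern.** A logistic regression needs a 0 or 1 for every analysed subject, and 7.3 puts every treated subject in the primary analysis. Followed literally, 7.2 gives some fully observed subjects neither value. They are not clinically odd: a subject rated much improved (CGI-I 2) whose CDRS-R is still 35 is an ordinary partial improver.

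Two analysts could therefore build different datasets from the same text. One would code these subjects as nonresponders. The other would leave them out because they fit neither definition. Leaving them out selects on a post-randomisation outcome, breaks intention-to-treat and, if the uncoded subjects are unevenly spread between arms, moves the estimated difference in either direction.

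The CGI-S term causes a second problem. A subject with CDRS-R below 28, CGI-I at most 2 and CGI-S of 3 or more enters Maintenance as a responder but is not a responder under 7.2. Nor does the plan say which rule the assumed 65% and 25% rates describe. Section 7.1 gives no cutoffs, and the 71% pilot rate it cites equals the 5 of 7 (71.4%) that section 1.3 reports as remission rated by the CDRS-R.

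**Working it through.** **Step 1. Enumerate the patterns.** Dichotomise CDRS-R (<28 / ≥28), CGI-I (≤2 / ≥3) and CGI-S (≤2 / ≥3), and apply the rules in 7.2 and in 3.1/6.3.

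| CDRS-R | CGI-I | CGI-S | 7.2 as written | 3.1 / 6.3 |
|---|---|---|---|---|
| <28 | ≤2 | ≤2 | response | responder |
| <28 | ≤2 | ≥3 | none | responder |
| <28 | ≥3 | ≤2 | none | nonresponder |
| <28 | ≥3 | ≥3 | none | nonresponder |
| ≥28 | ≤2 | ≤2 | none | nonresponder |
| ≥28 | ≤2 | ≥3 | none | nonresponder |
| ≥28 | ≥3 | ≤2 | nonresponse | nonresponder |
| ≥28 | ≥3 | ≥3 | nonresponse | nonresponder |

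Counts (response / nonresponse / uncoded):

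- 7.2 as written: 1 / 2 / 5.
- 7.2 with *and/or* in the nonresponse rule: 1 / 6 / 1. Row 2 stays uncoded because of the CGI-S term.
- Nonresponse defined as not meeting response: 1 / 7 / 0.

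**Step 2. Reproduce the stated power.** Inputs from 7.1: 65% versus 25%, 35 per group, two-sided 0.05. With the pooled normal approximation, power = Φ((|p₁ − p₂| − 1.96·SE₀)/SE₁).

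- SE₀ = √(0.45 × 0.55 × 2/35) = 0.1189
- SE₁ = √((0.65 × 0.35 + 0.25 × 0.75)/35) = 0.1089
- Power = Φ((0.40 − 0.2331)/0.1089) = 93.7%; the plan states 94%.

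At 25 per group the result is 83.2%; the plan states 83%. The power figures in 7.1 are therefore not in error. At the Summary's 38 active and 37 sham, power is 95.2%.

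**Step 3. What leaving subjects out would do (illustration).** The documents give no uncoded share. Let d be the assumed share, among subjects who miss response, with an uncoded pattern.

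- Number uncoded = 38 × 0.35 × d(active) + 37 × 0.75 × d(sham)
- Active rate after omission = (38 × 0.65)/(38 − 38 × 0.35 × d(active)); the sham rate is formed the same way.

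| d active / d sham | Uncoded of 75 | Rates after omission | Difference | Power |
|---|---|---|---|---|
| any, coded as nonresponse | – | 65% vs 25% | 40 points | 95.2% |
| 10% / 10% | 4.1 | 67.4% vs 27.0% | 40.3 | 94.2% |
| 20% / 20% | 8.2 | 69.9% vs 29.4% | 40.5 | 92.9% |
| 30% / 30% | 12.3 | 72.6% vs 32.3% | 40.4 | 91.1% |
| 30% / 10% | 6.8 | 72.6% vs 27.0% | 45.6 | 97.9% |
| 10% / 30% | 9.7 | 67.4% vs 32.3% | 35.1 | 82.0% |

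**Step 4. The CGI-S term (illustration).** Suppose the 65% and 25% were two-scale rates, which the plan does not say, and some responders then fail CGI-S. At 38/37:

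| Responders lost, active / sham | Rates | Power |
|---|---|---|
| 10% / 10% | 58.5% vs 22.5% | 90.4% |
| 20% / 20% | 52% vs 20% | 83.7% |
| 30% / 30% | 45.5% vs 17.5% | 75.2% |
| 5% / 30% | 61.75% vs 17.5% | 98.6% |
| 20% / 5% | 52% vs 23.75% | 72.1% |

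The effect on power is unknown in both size and direction.

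**The case against.** The strongest reply is that harm needs an unlikely reading. Section 7.2 offers two labels for a logistic regression, 7.3 keeps every treated subject, and 3.1 and 6.3 already class four of the five uncoded patterns as nonresponders. Nothing instructs an analyst to discard anyone. Coding everyone else as nonresponse is indeed the natural reading, and under it nothing changes. But 7.2 states a different rule, and row 2 stays uncoded even when *and/or* is imported.

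Second, 5 of 8 counts patterns, not subjects. Entry requires CDRS-R of at least 40, so a subject below 28 has fallen by at least 13 points; CGI-I of 3 or more after such a fall is possible but probably rare. This is fair, and the share of subjects is unknown.

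Third, some of the CGI-S evidence is soft. The Summary's list of primary measures is not worded as exhaustive, 7.1 may be shorthand, and 1.3 does not say that the pilot used the CDRS-R alone. The firm conflict is between 7.2 and the rules in 3.1 and 6.3. Because 7.2 calls the Phase II analysis exploratory, that conflict mainly affects labels and reporting. A separate allocation rule for Phase II would be legitimate if the plan said so.

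These points limit the weight of the concern but leave the defect in place.

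**Conclusion.** The concern holds. As written, 7.2 leaves 5 of 8 score patterns without a code, or 1 of 8 if *and* is read as *and/or*, and no other section supplies the missing rule for the analysis. The enumeration is exact and rests on no assumption.

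The consequence for the estimate depends on a choice the plan leaves open. Coding the uncoded subjects as nonresponders gives the intended comparison. Leaving them out in equal shares keeps the difference near 40 points, with power of 91% to 94%. Leaving them out unevenly moves the difference by about 5 points either way under the assumed 10% and 30% shares.

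The stated 94% power stands for whichever rule the 65% and 25% describe, but the plan does not identify that rule. The other powered endpoint, continuous CDRS-R change, is untouched. This should be fixed, with high confidence in the defect and no claim about how many subjects it would affect.

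**What to change.** Make both changes before unblinding.

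1. **In 7.2, replace the nonresponse rule** with: *Nonresponse: all subjects not meeting the response criteria.* This codes all 8 patterns. It costs one clause and leaves the 7.2 responder count unchanged.

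2. **Use one response rule, with cutoffs, in 7.1 and 7.2.** The sponsor chooses between:
   - **A. CDRS-R <28 and CGI-I ≤2.** This is already the rule in 3.1 and 6.3, matches the scales named in 7.1 and the Summary, and makes remission (which adds CGI-S ≤2) distinct from response. The Summary should then say that remitters count as responders in the binary analysis. Downside: the endpoint is more lenient than 7.2 now states, so the response rate in each arm can only stay the same or rise.
   - **B. Keep CGI-S ≤2.** State in 7.1 that the 65% and 25% rates and the 94% power refer to the three-scale rule, remove remission as a separate level in the Summary, and say in 3.1 and 6.3 that Phase II assignment uses its own two-scale rule. Downside: Phase II responders and analysis responders remain different groups, and the sponsor must justify 65% and 25% for the stricter rule.

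Either option is a wording amendment. Neither needs new data, and the sample size stands if the 65% and 25% rates apply to the rule chosen.
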